#### Sample Size Considerations:

The proposed sample size for this one year study is a total of 154 evaluable subjects (n=77 randomized to each voiding group). A subject will be "evaluable" if she gets randomized and is able to undergo the voiding trial. A subject who is not able to undergo the voiding trial is considered "not evaluable" and would not be included in the analysis.

The study will be designed as a non-inferiority trial, where the FAST voiding trial will be considered non-inferior to the Traditional voiding trial if the difference in the rate of catheterization between the two groups within the six-week post-operative period among patients discharged without a catheter is less than  $\delta$ =10% (i.e.  $\delta$ =10%, the margin of non-inferiority). More formally, if the rates of catheterization during the six-week post-operative period are p\_F and p\_T, respectively for the FAST and Traditional voiding methods, then the null (Ho) and alternative hypotheses (HA) are:

$$H_0$$
:  $d = p_F - p_T \ge \delta$  vs.  
 $H_A$ :  $d = p_F - p_T < \delta$ 

Based on the investigators' clinical experience, it can be reasonably assumed that among those who pass the Traditional retrograde fill voiding trial, the rate of catheterization during the six-week post-operative period is about 5%. Further assuming that the rate of catheterization among those who pass the FAST voiding trial is the same as in the traditional voiding test (i.e. 5% as well), and using a non-inferiority margin, $\delta$ , of 10%, then a sample size of 59 per group (n=118 total) will yield 80% power to determine that the FAST voiding trial is not inferior to the Traditional voiding trial (alpha=0.05).

Based on published manuscripts, about 30% of evaluable patients will fail either voiding trial, that is, approximately 30% in the traditional retrograde fill voiding trial arm will fail the test and similarly, approximately 30% in the FAST voiding trial arm will fail the test. Therefore, in order to obtain 118 subjects who pass the voiding test (59 per group), we would need to have a total of 154 subjects (118 x 1.3=154).

Randomized subjects will fall into three groups:

- 1. Subjects with a complication at surgery that would require prolonged catheterization immediately postoperative.
- 2. Subjects who fail either voiding test and are discharged home with a catheter (expected to be 25-26% based on pusblished manuscripts)
- Subjects passing either trial of void and discharged home without a
  catheter. This is the main population of interest that we want to
  examine to identify what proportion of subjects would end up
  needing a catheter ultimately in the 6-week postoperative period.

Below is a tabulation of sample size requirements for 80% power, using various assumptions for the rates of catheterization during the six-week post-operative period in each of the two

Version Date: 2/26/16 Page 12 of 25

voiding methods, using a 2-sided alpha level of 0.05, and a non-inferiority margin,  $\delta$ , of 10%:

Traditional	FAST Voiding	Sample Size
Voiding Method	Method	Per Method (N)
0.05	0.07	109
0.05	0.06	80
0.05	0.05	59
0.05	0.04	44
0.05	0.03	33

Version Date: 2/26/16 Page 13 of 25

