## **Statistical Methods:**

1. For the primary objective:

The test for non-inferiority will be carried out using a two-tailed 95% confidence interval for the difference in the rate of catheterization between the two voiding methods, within the six-week post-operative period,  $\delta$  ( $\delta$ =rate of catheterization in the FAST voiding trial – rate of catheterization in the Traditional voiding trial). This difference,  $\delta$ , is the margin of non-inferiority and will be set at 10%. If the upper confidence limit for the difference is  $<\delta$  ( $\ge\delta$ ) then we will conclude that the FAST voiding trial is non-inferior (inferior) to the Traditional voiding trial.

The test for non-inferiority will be performed only for the primary outcome variable of interest, i.e., catheterization within the six-week post-operative period among subjects who were discharged without needing a urinary catheter.

The test for non-inferiority will also be performed according to surgery type (the stratification variable).

- For the secondary objectives:
  - a. The chi-square test or Fisher's exact test, as appropriate, will be used to compare the two voiding methods with respect to the proportion of subjects who are sent home with a catheter due to failure of their voiding trial, post-surgery.
  - b. The chi-square test or Fisher's exact test, as appropriate, will be used to compare the two voiding methods with respect to the proportion of subjects who present with any UTI within the six-week post-operative period. If feasible, the incidence of UTIs will be compared between the two voiding methods using the Incidence Density Ratio Method, or if feasible, Poisson regression methods.
  - c. The chi-square test or Fisher's exact test, as appropriate, will be used to compare the two voiding methods with respect to the proportion of subjects who present to the emergency room or the urogynecology clinic (unexpectedly) due to voiding dysfunction or suspected infection, within the six-week post-operative period. If feasible, the incidence of ER visits or unexpected clinic visits will be compared between the two voiding methods using the Incidence Density Ratio Method, or if feasible, Poisson regression methods.

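### The 59 per group was calculated at one-sided alpha 0.05, but the planned two-tailed 95% confidence interval tests at one-sided 0.025, so under the plan's own 5% assumption power is about 70%, not 80%

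*Combined protocol and SAP*

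**What the plan says.** Three places in Section 12 of the combined protocol and SAP bear on this.

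- **Statistical Methods**, primary objective: "The test for non-inferiority will be carried out using a two-tailed 95% confidence interval for the difference in the rate of catheterization". FAST is declared non-inferior if the upper limit is below 10 percentage points, and inferior if the limit is at or above that value.
- **Sample Size Considerations**, text: with a 5% rate among those who pass the traditional trial, and a FAST rate that "is the same as in the traditional voiding test (i.e. 5% as well"), "a sample size of 59 per group (n=118 total) will yield 80% power" to show that FAST is "not inferior to the Traditional voiding trial (alpha=0.05"). This sentence does not say whether alpha is one- or two-sided. The hypotheses set out just above it are one-sided.
- **Sample Size Considerations**, table: five scenarios, including the same 59, are tabulated for 80% power "using a 2-sided alpha level of 0.05" and a 10% margin.

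**The concern.** Comparing the upper limit of a two-tailed 95% interval with a margin is a one-sided test at 0.025, with critical value 1.96. A two-sided alpha of 0.05 means the same thing in the non-inferiority direction. So wherever the plan specifies sidedness, the calculation should use 1.96. An n of 59 looks too small for that.

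This is the plan's only power claim for its only formal non-inferiority endpoint, and the 59 feeds directly into the totals of 118 and 154. If it rests on a weaker test than the one to be run, the trial is more likely than stated to miss non-inferiority when it is true. The consequence is sharper here because the decision rule labels such a miss as FAST being inferior. An unresolved conflict also leaves room to choose between a 90% and a 95% interval after the results are known, and that choice could decide the outcome.

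**Working it through.** **Inputs, all from Section 12.** Traditional rate pT = 0.05; FAST rate pF = 0.05 in the base case and 0.03 to 0.07 in the table; margin 0.10; power 80% (z = 0.8416); 1:1 allocation.

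**Formula** (unpooled normal approximation):

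n per group = (z_α + 0.8416)² × [pT(1 − pT) + pF(1 − pF)] / [0.10 − (pF − pT)]²

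**Step 1: reproduce the plan's figure.** In the base case the variance term is 2 × 0.05 × 0.95 = 0.095.

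- z_α = 1.645 (one-sided 0.05): (2.4865)² × 0.095 / 0.01 = 58.73, rounded up to 59. This is the plan's number.
- z_α = 1.960 (one-sided 0.025): (2.8016)² × 0.095 / 0.01 = 74.56, rounded up to 75.

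**Step 2: the whole table.**

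| pT | pF | Plan's n | n at z = 1.645 | n at z = 1.960 | Power of plan's n with 95% CI |
|---|---|---|---|---|---|
| 0.05 | 0.07 | 109 | 108.77 → 109 | 138.09 → 139 | 70.2% |
| 0.05 | 0.06 | 80 | 79.30 → 80 | 100.68 → 101 | 70.5% |
| 0.05 | 0.05 | 59 | 58.73 → 59 | 74.56 → 75 | 70.3% |
| 0.05 | 0.04 | 44 | 43.89 → 44 | 55.72 → 56 | 70.2% |
| 0.05 | 0.03 | 33 | 32.89 → 33 | 41.75 → 42 | 70.2% |

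All five entries match at one-sided 0.05 and none matches at one-sided 0.025. Two other formulas do not give 59 at one-sided 0.025 either. The Farrington-Manning score formula gives 99.4 at one-sided 0.025, and 77.2 even at one-sided 0.05. A continuity-corrected version gives about 78 at one-sided 0.05.

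**Step 3: power of 59 per group.** Power = Φ(0.10 / √(0.095/59) − z_α), where √(0.095/59) = 0.0401 and 0.10/0.0401 = 2.492.

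- One-sided 0.05: Φ(2.492 − 1.645) = Φ(0.847) = 80.2%.
- One-sided 0.025, as planned: Φ(2.492 − 1.960) = Φ(0.532) = 70.3%.

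**Step 4: exact binomial check at 59 per group, 5% in both arms.** The plan does not name an interval method, so the methods below are assumptions.

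| Interval | Two-sided 90% | Two-sided 95% |
|---|---|---|
| Wald | 79.3% | 71.4% |
| Newcombe | 73.0% | 58.6% |
| Farrington-Manning score | 73.0% | 55.1% |

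The Wald row confirms the planning formula. The other rows mix two effects. Changing the interval method alone takes power from about 79% to 73% at the 90% level, so the fall to 55–59% is not all due to alpha. The effect of the alpha mismatch on the plan's own formula is 80.2% − 70.3%, about 10 points.

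**The case against.** The strongest points on the other side are these.

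- **The error is in the safe direction.** The 95% interval is the stricter test, so a false claim of non-inferiority does not become more likely. This is correct. The primary test is coherent as written, and the fault lies in the power statement and the table. That does not make the 80% true.
- **The text's alpha could be one-sided.** The hypotheses are one-sided and the sentence gives no sidedness, so read alone it fits a one-sided 0.05 calculation. That is fair, and it is probably how the numbers arose. But then the table's two-sided label is wrong and the analysis should specify a 90% interval. The sections conflict on either reading.
- **70% depends on the 5% rate, which comes from clinical experience.** With 59 per group and the 95% interval, the same formula gives about 79% power if both rates are 4% and 89% if both are 3%. This stands as a condition on the 70%. It does not rescue the plan's claim, which was made at 5%.
- **Score-type figures overstate the problem.** They rest on an interval method the plan does not name and carry an effect separate from alpha. Accepted: they show that 70% is the favourable case, but they are not the size of this error.

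**Conclusion.** The concern holds. The table was evidently computed at one-sided 0.05. The documents do not say this, but five exact matches out of five leave little doubt. The table's label and the analysis rule both require one-sided 0.025.

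Given 5% in both arms, a 10-point margin and 59 evaluable passers in each group, power under the planned analysis is about 70%. The risk of missing true non-inferiority is about 30% rather than 20%, and under the stated decision rule each miss would be reported as inferiority. Eighty per cent power needs 75 passers per group (150 in all), not 59 (118). With a Newcombe or score interval, power at 59 per group would be lower still. The result also takes the 118 passers as obtained; whether 154 evaluable subjects would supply them is a separate question.

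**What to change.** **Preferred.** In Section 12, keep the two-tailed 95% interval and state that it corresponds to a one-sided 0.025 test. Restate the power of 59 passers per group as about 70% at 5% in both arms, and correct the table to 139, 101, 75, 56 and 42. Name the interval method, since power depends on it. The cost is some wording and one table, with no extra patients, and the stated power becomes less favourable.

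**If one-sided 0.05 was intended.** Say so in the text and the table heading, justify the level, and change the analysis to a two-sided 90% interval. This is the weaker route because it relaxes the type I error to fit the calculation. With a Wald limit and true rates of 15% against 5%, the exact chance of wrongly declaring non-inferiority at 59 per group is about 6.5% with a 90% interval, against 3.4% with a 95% interval. The choice must be made before outcome data are seen.

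**If 80% power with the 95% interval is to be kept.** Plan for 75 passers per group by the plan's own formula. This is the costly option. At the plan's 30% failure rate it means 150/0.70 = 214.3, so 215 evaluable subjects; at 26% failure, 150/0.74 = 202.7, so 203. Section 5 gives about 200 eligible operations a year, so recruitment would run beyond the planned 12 months.

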#### 8. NUMBER OF SUBJECTS

- Indicate the total number of subjects to be accrued locally. If applicable, distinguish between the number of subjects who are expected to be pre-screened, enrolled (consent obtained), randomized and complete the research procedures.
- If your study includes different cohorts, include the total number of subjects in each cohort.
- If this is multisite study, include total number of subjects across all sites.

The proposed sample size for this one year study is a total of 154 evaluable subjects (n=77 randomized to each voiding group). A subject will be "evaluable" if she gets randomized and is able to undergo the voiding trial. A subject who is not able to undergo the voiding trial is considered "not evaluable" and would not be included in the analysis.

Version Date: 2/26/16 Page 6 of 25

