#### **Randomization:**

Subjects will be randomized in a 1-1 ratio to either the Traditional voiding trial or the FAST voiding trial. Randomization will be stratified by site (North Shore or Long Island Jewish), and within each site, by surgical type (apical prolapse surgery without sling or apical prolapse surgery with sling).

The Biostatistics Unit at the Feinstein Institute for Medical Research [BU-FIMR] will develop a randomization plan using the Biostatistics Randomization Management System [BRMS]. BRMS is a secure, HIPAA-compliant, web-based application that allows investigators to randomize subjects into randomized clinical trials (RCTs) using a personal computer with internet access. Randomization notifications are automatically sent to the PI and other authorized personnel. BRMS maintains compliance in RCTs. Details of the randomization procedure will be further developed upon approval of the protocol.

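### The 30% failure allowance is applied by multiplying by 1.3 instead of dividing by 0.70, so 154 evaluable subjects are expected to give about 108 voiding-trial passers, not 118

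*Combined protocol and SAP*

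**What the plan says.** Section 12, Sample Size Considerations, ties 80% power to 59 passers per group, assuming a 5% catheterization rate in both arms and a 10-point margin. It then allows for women who fail the voiding trial. It states that "about 30% of evaluable patients will fail either voiding trial", and says the same rate applies in each arm. The stated purpose of the allowance is "in order to obtain 118 subjects who pass the voiding test (59 per group"). The inflation step that follows from it reads: "we would need to have a total of 154 subjects (118 x 1.3=154").

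Sections 8 and 12 both define the 154 as evaluable subjects, meaning randomized and able to undergo the voiding trial. Section 8 gives the allocation as "n=77 randomized to each voiding group".

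Later in Sample Size Considerations a second failure rate appears, for subjects "discharged home with a catheter (expected to be 25-26% based on pusblished manuscripts").

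**The concern.** The 30% and the 154 share a denominator: evaluable patients. The number N needed to obtain 118 passers therefore solves N x 0.70 = 118. Multiplying 118 by 1.3 adds 30% of the passers instead, which is too little.

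The non-inferiority test is confined to women discharged without a catheter, so a shortfall in passers is a shortfall in the primary analysis set. The plan has no interim analysis and describes no sample-size re-estimation that would reveal the gap during the trial. The enrolment target in Section 8 carries the same number.

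**Working it through.** **Inputs, all from Section 12**
- 59 passers per group, 118 in total, for 80% power (Sample Size Considerations)
- failure rate 30% of evaluable patients; also 25-26% (same section)
- catheterization 5% in both arms among passers (same section); margin 10 points (Statistical Methods)
- "Subjects will be randomized in a 1-1 ratio" (Randomization)
- "The test for non-inferiority will be carried out using a two-tailed 95% confidence interval" (Statistical Methods), equivalent to one-sided 0.025

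**1. Reproducing the plan's figures**

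With unpooled variance, n per group = [pT(1 - pT) + pF(1 - pF)] x (z_alpha + z_0.80)^2 / [0.10 - (pF - pT)]^2.

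| pT | pF | Plan | One-sided 0.05 | One-sided 0.025 |
|---|---|---|---|---|
| 0.05 | 0.07 | 109 | 108.8 → 109 | 139 |
| 0.05 | 0.06 | 80 | 79.3 → 80 | 101 |
| 0.05 | 0.05 | 59 | 58.7 → 59 | 75 |
| 0.05 | 0.04 | 44 | 43.9 → 44 | 56 |
| 0.05 | 0.03 | 33 | 32.9 → 33 | 42 |

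So the 59 is reproduced, but only at one-sided 0.05, although the plan labels its alpha two-sided. That the plan used one-sided 0.05 is an inference from this match. The 154 is reproduced as 118 x 1.3 = 153.4, rounded up.

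**2. Expected passers from 154 evaluable**
- 30% failure: 154 x 0.70 = 107.8; per group 77 x 0.70 = 53.9, about 54
- 26% failure: 154 x 0.74 = 113.96, about 57 per group
- 25% failure: 154 x 0.75 = 115.5, about 58 per group
- failure rate at which 154 gives 118: 1 - 118/154 = 23.4%, a rate the plan does not state

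At 30% failure, the binomial probability that 154 evaluable subjects give at least 118 passers is about 4%.

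**3. Evaluable subjects needed for 59 passers per group**
- 30% failure: 118/0.70 = 168.6; per group 59/0.70 = 84.3, so 85 per group, 170 in total
- 25-26% failure: 59/0.75 = 78.7 and 59/0.74 = 79.7, so 79-80 per group, 158-160 in total

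**4. Effect on power**

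Power = Phi(0.10/SE - z), with SE = sqrt(2 x 0.05 x 0.95/n).

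| Passers per group | One-sided 0.05 (z = 1.645) | Two-tailed 95% interval (z = 1.960) |
|---|---|---|
| 59 (claimed) | 80.2% | 70.3% |
| 57.75 (25% failure) | 79.4% | 69.3% |
| 57 (26% failure) | 79.0% | 68.8% |
| 54 (30% failure) | 77.0% | 66.4% |

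Reading down a column gives the effect of the inflation slip: 3-4 points at 30% failure and about 1 point at 25-26%. Reading across a row gives the effect of the alpha mismatch, about 10 points, which is a separate matter. Letting the number of passers vary as Binomial(77, 0.70) in each arm changes little: 76.8% and 66.2%.

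**The case against.** The arithmetic is hard to dispute; the size of the effect is more open.

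- **The power loss depends on the approximation.** Exact enumeration for the Wald interval gives 79.3% at 59 per group and 79.2% at 54 (one-sided 0.05), and 71.4% and 70.9% for the two-tailed 95% interval. At these two values of n the loss almost vanishes. That is correct, but exact power moves in steps: at one-sided 0.05 it is 75.9% at 52, 79.6% at 53, 79.8% at 58 and 82.7% at 60. A comparison of two particular values can therefore hide the downward trend. The plan does not name its interval method, so the power figures are approximate.
- **The published failure rates are lower than 30%.** Section 3 reports catheterization of 25.5% and 26% in the earlier sling trial, and Section 12 repeats 25-26%. At those rates the shortfall is only 2.5 to 4 passers. This stands as a limit on the size of the effect, but the plan chose 30% for its calculation, and neither rate makes 154 sufficient.
- **The slip does not threaten the design.** This also stands: population, margin and test are untouched. But the claim that 154 yields 118 passers remains wrong, and it supports the power statement.

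**Conclusion.** The concern holds. On the plan's own 30%, 154 evaluable subjects are expected to yield about 108 passers (54 per group), 10 fewer than stated. Equivalently, each arm is 8 evaluable subjects short (77 against 85). At 5% catheterization in both arms, and by the normal approximation, this alone costs 3-4 points of power; at 25-26% failure it costs about 1 point. The effect is modest, but the sample-size statement is incorrect as written and needs correction. Most of the distance from 80% to about 66% comes from sizing at one-sided 0.05 while planning a two-tailed 95% interval, and should not be attributed to this slip.

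**What to change.** In Section 12, Sample Size Considerations, choose one failure rate (30% or 25-26%) and use it throughout. Replace the multiplication by 1.3 with division by the pass proportion, showing that 118 passers require 118/0.70 evaluable subjects at 30% failure. Then take one of two routes.

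- **Keep 154 (77 per group).** State that 154 x 0.70, about 108 passers (54 per group), are expected. Replace the 80% with the matching power: about 66% for the planned two-tailed 95% interval, with 77% given as the one-sided 0.05 figure so that the two effects stay distinct. If 25-26% is chosen, the figures are 57-58 per group, 68.8-69.3% and 79.0-79.4%. This costs wording in Section 12 only; Section 8 is unchanged.
- **Deliver 118 passers.** Set 85 per group, 170 evaluable (79-80 per group, 158-160 in total, if 25-26% is chosen), and change the totals in Sections 8 and 12 by amendment. At 30% this adds 16 evaluable patients. Section 5 reports about 200 such surgeries in 12 months, so 170 is 85% of them (154 is already 77%) before refusals and exclusions. Sections 5 and 9 should therefore be rechecked. Do not repeat the 80% beside 170 until alpha is settled: 59 passers per group gives about 70% under the planned interval.

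The second route is optional; correcting the statement is not.

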#### 13. SPECIMEN BANKING

- If specimens will be banked for future research, describe where the specimens will be stored, how long they will be stored, how they will be accessed and who will have access to the specimens
- List the information that will be stored with each specimen, including how specimens are labeled/coded
- Describe the procedures to release the specimens, including: the process to request release, approvals required for release, who can obtain the specimens, and the information to be provided with the specimens.

*Not applicable* 

## 14. DATA MANAGEMENT AND CONFIDENTIALITY

- Describe the data and specimens to be sent out or received. As applicable, describe:
  - What information will be included in that data or associated with the specimens?
  - Where and how data and specimens will be stored?
  - How long the data will be stored?
  - Who will have access to the data?
  - Who is responsible for receipt or transmission of data and specimens?
- Describe the steps that will be taken to secure the data during storage, use and transmission.

#### **Data Management**

REDCap (Research Electronic Data Capture), a secure, web-based application, will be used to store data from the trial.

### Confidentiality

Confidentiality will be maintained by using patient identification numbers instead of names.

#### Storing Documents in Hard Copy

Original documents including consent forms that contain subjects' PHI, as well as questionnaires, will be stored in a locked cabinet within the office of Urogynecology, [name]. These documents will be kept separately from any de-identified research data that will be stored electronically as mentioned below. IRB approved investigators will be the only individuals with access to research data that contains PHI.

